Finally, once a participant signs the consent form, the investigator will perform a focused review of the participant's medical record (including laboratory data) to again confirm that the patient has HF, and will consult with the study cardiologist in the event that there is any need for further clarification. If there is question about the patient's medical prognosis (to assess whether the patient has a condition likely to lead to death within 6 months) the study team will consult with the patient's inpatient or outpatient team and/or the study cardiologist. Participants will be asked to sign a release form at the time of consent to allow study staff to discuss their diagnosis and aforementioned medical variables during the study.

Partners Healthcare has an electronic system that lets the participants' study doctors know if they are admitted to a Partners Hospital, or if they visit a Partners Hospital Emergency Department. We will

use this system to ensure that the study doctors know about any possible problems or side effects participants experience while taking part in the study.

C. Treatment assignment/randomization

There is no randomization procedure required for this trial.

V. STUDY PROCEDURES

A. Study visits/evaluations (See Table 1)

Initial visit (Week 1; in person). The initial visit will occur in an MGH inpatient unit, in the outpatient cardiac clinic, in a designated private office within the CPRP suite (for those contacted via opt-out letter), or over the phone (if a participant prefers to not come to the hospital for an in-person visit). Participants will meet with a member of the study staff (the study “trainer”) and complete self-report questionnaires. These questionnaires assess optimism (Life Orientation Test-Revised; LOT-R),⁵⁵ anxiety/depression (Hospital Anxiety and Depression Scale; HADS),⁵⁶ positive emotions (Positive and Negative Affect Schedule; PANAS),⁶⁵ health-related quality of life (MOS Short Form-12; SF-12),⁵⁷ cardiac symptoms and heart failure-related quality of life (Kansas City Cardiomyopathy Questionnaire; KCCQ),^{58,59} medication adherence (Self-Reported Medication Adherence [adapted from the Heart and Soul Study]; SRMA),⁶⁰ and sodium intake (Scored Sodium Questionnaire; SSQ).⁶¹ Participants will also answer questions about their alcohol (using the AUDIT-C)⁶² and cigarette use. In sum, these scales should take approximately 30 minutes to complete.

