ActiGraph accelerometers are validated as measures of physical activity and have been used in numerous studies of physical activity in patients with medical illness.⁶⁴ The accelerometer is a small 1.5" square device that can be worn on an elastic band (around the lower waist) or clipped onto a belt. It tracks the number of steps taken. After explaining how to use the accelerometer, the study trainer will schedule an appointment to call the participant in 1 week to review the first exercise. In total this initial visit will take approximately 50-60 minutes.

Weekly phone sessions (Weeks 1-10). All participants will be asked to complete 9 weekly PP exercises and will be asked to speak with a study trainer weekly. In addition, in Week 10, there will be a wrap-up phone call that focuses on the progress the participant has made in the program and makes a plan for continuing to use PP skills and engage in healthy activities in the future. Weekly phone sessions will last approximately 30 minutes. These calls will be recorded so that a percentage (10%) of these recordings can be reviewed to ensure that the PP and goal-setting portions of the intervention are being delivered as described in the protocol and trainer manual.

Program Content. All phone sessions will include (a) a review of the week's PP exercise (including the participant's ratings of pre- and post-exercise happiness, ease and helpfulness of the exercise, and optimism related to the future), (b) a discussion of the rationale of the next week's PP exercise through a guided review of the PP manual, and (c) assignment of the next week's PP exercise. Additionally for the goal-setting portion, participants will (a) review their goals and behaviors from the prior week, (b) discuss techniques for improving health behavior adherence (e.g., monitoring physical activity, reading nutrition labels), and (c) set goals for the next week. The exercises and content for both PP and MI will be assigned in the same order for all participants receiving them. During the calls, the trainer and participant will also review the next section of the treatment manual and prepare for the upcoming week's exercise.

Positive Psychology Exercises. The PP exercises used in this study were selected based on their superior performance in our pre-pilot research and others' work. They will be grouped into three-week modules focusing on a different psychological state:

Module 1: Gratitude-based activities

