We will ask participants to report adverse events related to study participation they may have experienced at any time throughout the study. Any adverse events will be reported to the PI and to the IRB according to Partners HRC guidelines.

E. Radiation risks

There will be no radiation exposure in this study.

VI. POTENTIAL BENEFITS

A. Potential Benefits to Participants

It is possible that participants will not receive benefit from participation. Patients will undergo a series of exercises that are designed to increase optimism, improve well-being, and potentially improve cardiac health behaviors. Analyses of PP studies have been that these interventions are associated with improved psychological well-being and decreased depressive symptoms, and optimism

is associated with superior medical outcomes. Therefore, participating individuals may benefit by having improvements in these important and clinically relevant outcomes. Overall, contact with study trainers and the systematic follow-up assessments may also provide support and social connection for participants at a time of recent medical crisis. This may be an improvement over no such contact or systematic evaluation, as is current standard practice.

Patients will be given the opportunity to identify positive emotions and consider ways to enhance their own positive emotions. Description of the PP exercises may enlighten them as to potential means of improving their own emotional states. Furthermore, they will have the opportunity to consider possible barriers to adherence to health-related behaviors.

B. Potential Benefits to Society

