Monitoring mechanism: [name] (PI) will take primary responsibility for the data safety monitoring. However, this study will have a formal data safety monitoring board (DSMB), which will be chaired by [name] (psychiatry, primary mentor), and populated by [name] (psychology, co-mentor), [name] (cardiology, external to study), and [name] (psychology, external to study).

Monitoring intervals: Monitoring of adverse events will occur on an ongoing basis with notification of [name] with any adverse study-related events. More systematic weekly meetings for review of feasibility/acceptability information and minor IRB deviations will be held between [name] and study staff, including the lead research coordinator. [name] will then discuss any potential issues regarding data safety or protocol deviations with [name] during weekly supervision meetings. This allows the team to review this information and make adjustments to procedures as required. Furthermore, weekly journal clubs are held with the study team; these include discussions of related projects (e.g., studies of physical activity in cardiac patients, studies of positive psychological interventions) and the general psychiatry and cardiology literature. Finally, the formal DSMB will meet every four months to monitor patient safety outcomes. These ongoing, weekly, and intermittent reviews ensure that the study procedures minimize research-related risk by reviewing specific outcomes linked to the project and by reviewing relevant literature to ensure that interventions are best practice. [name] (study PI) is responsible for directly reporting serious study-related adverse events to the NIH/NHLBI, and even if there are no such events, a yearly report summarizing adherence to the DSMP, review of study-related enrollment and issues during the study period, and any relevant changes to the protocol, will be sent to NHLBI.

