Information to be monitored: Information to be monitored will include: (a) an evaluation of the progress of the research study, including assessments of data quality and timeliness and participant recruitment, accrual and retention consistent with plans for diversity and generalizability, (b) a review of study safety data—adverse event (and minor deviation) information—to determine whether the study should continue as originally designed, be changed, or be stopped, (c) review of procedures to maintain participant confidentiality (e.g., storage of identifiable information in locked cabinets, ensuring study databases have no personal identifying information, use of study participant numbers on communications about the study), and (d) an assessment of external factors or relevant information (e.g., developments in the literature, results of related studies, etc.) that may have an impact on the safety of participants or on the ethics of the research study, such as through the journal club listed above.

C. Outcomes Monitoring

As noted above, this study is a proof-of-concept trial to determine if all aspects of the protocol are feasible, acceptable, and effective. After 5 participants have completed the trial, we will briefly review the study and our outcomes. If participants' acceptability scores in the PP group are low (or optimism scores decrease following the exercises), or we sense more generally that some participants have been dissatisfied with the program, we will likely alter the protocol to address these issues. Similarly, if our rates of session completion are far below expected rates, we will reassess our protocol and likely make substantial changes. We will then complete the more formal data analysis once 10 participants have completed the trial.

On a weekly basis, the research team will meet to review study progress. At that time, the principal investigator will review informed consent documents, study forms, and procedures completed

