that week, as well as all chart review forms performed that week for completeness and accuracy. The study team will also discuss any procedural difficulties, recruitment issues, and adverse events at this meeting (and before if needed). Investigators will also review consent documents and address acute issues in real time throughout the week. We will take several measures to ensure the integrity of data collection/entry/analysis and the fidelity of our intervention. [name] will periodically review the recordings of weekly phone calls to ensure their fidelity.

D. Adverse event reporting guidelines

We will follow all PHRC guidelines with respect to reporting unanticipated problems, including adverse events. Specifically, when a serious or nonserious adverse event occurs, the PI will review the event to determine if it was possibly or definitely related to participation in the research. For all unanticipated problems and adverse events deemed related or possibly related to the research, we will complete and submit an Other Event report through Insight/eIRB as soon as possible and within 5 working days/7 calendar days (as defined in the March 2014 Reporting Unanticipated Problems Including Adverse Events report). At Continuing Review, we will provide a summary of all unanticipated problems as per PHRC protocol. Finally, if there are unanticipated problems, especially if serious or recurrent, the PI ([name]) will amend the protocol if it is deemed necessary to protect the safety and welfare of the participants.

IX. REFERENCES

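### The adverse event question makes participants pre-judge relatedness, and the protocol's other detection routes recover only some of the events this screens out

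*Combined protocol and SAP*

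**What the plan says.** Three statements govern how an adverse event becomes known and is judged.

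- **Solicitation (VII.D, closing paragraph):** "We will ask participants to report adverse events related to study participation they may have experienced at any time throughout the study". The next sentence covers onward reporting: "Any adverse events will be reported to the PI and to the IRB according to Partners HRC guidelines".
- **Ongoing monitoring (VIII.B, Monitoring intervals):** the responsible person is to be notified "with any adverse study-related events".
- **Relatedness (VIII.D):** "when a serious or nonserious adverse event occurs, the PI will review the event to determine if it was possibly or definitely related" to the research. Unanticipated problems and events judged related or possibly related then go to the IRB within 5 working days/7 calendar days.

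The protocol also has routes that do not depend on the participant's view of cause. IV.B describes an electronic system that lets "study doctors know if they are admitted to a Partners Hospital, or if they visit a Partners Hospital Emergency Department", and says it will be used to learn of problems during the study. The Week 10 follow-up call (V.A) asks about readmissions for cardiac causes. VII.D directs patients who report acute symptoms to emergency care.

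Under VIII.B (Information to be monitored), adverse event information is reviewed "to determine whether the study should continue as originally designed, be changed, or be stopped".

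**The concern.** The PI can judge only the events that reach the PI. If participants are asked solely for events they tie to the study, the judgement that VIII.D reserves for the PI has already been made, by someone less able to make it.

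That matters here because the intervention includes individual physical activity goals (V.A, Goal-setting) for patients with NYHA class I to III heart failure, some recruited as inpatients (III.B). Breathlessness, dizziness, a fall or a joint injury in such a patient is easily put down to heart failure or age. Section VII names no risk from increased activity that might prompt the participant to make the link. The consent form is not among the documents reviewed and may say more.

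At stake is how complete the information is on which the PI and the DSMB decide whether the study continues, changes or stops. The primary feasibility result is not affected.

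**Working it through.** The documents state no event rate or count on this point, so no calculation applies. The check sets the passages side by side.

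**Step 1: order of events.** VII.D decides what participants are asked. VIII.D decides what happens once an event is known, when "the PI will review the event to determine if it was possibly or definitely related to participation in the research". The restriction in VII.D therefore acts first. VIII.B applies a similar restriction to ongoing notification, again ahead of the VIII.D review.

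**Step 2: does the second sentence of VII.D undo the restriction?** It covers any adverse event without limit, but only for reporting onward what is already known. It does not widen the question put to participants.

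**Step 3: what the other routes catch.**

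| Route | Catches regardless of attribution | Leaves out |
|---|---|---|
| Electronic alert (IV.B) | Partners admissions and emergency visits | Care outside Partners; anything managed at home or in clinic |
| Week 10 question (V.A) | Readmissions for cardiac causes | Non-cardiac admissions; emergency visits without admission; participants not reached at Week 10 |
| Acute symptoms (VII.D) | Acute symptoms a patient chooses to report | Symptoms not volunteered; described as emergency handling, not event recording |
| Weekly calls (V.A, Program Content) | Whatever comes up incidentally | No health-event question among the listed content |

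On the last row, the text says "All phone sessions will include (a) a review of" the week's exercise and ratings, followed by the rationale and assignment of the next exercise and the goal-setting review. Nothing in that list asks about health events.

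Two details limit the first two routes. III.B allows participants to do all visits by phone, so care outside Partners is foreseeable. Section VI.D allows up to 15 enrolled to obtain 10 completers, so up to 15 − 10 = 5 people might never be asked the Week 10 question. Neither the alert nor the Week 10 answer is expressly said to be recorded as an adverse event.

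**Step 4: what remains.** When the participant does not link them to the study, no described procedure solicits:

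- nonserious events;
- falls, injuries or symptoms managed at home or in clinic;
- emergency visits outside Partners;
- non-cardiac admissions elsewhere.

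**Step 5: scale.** How many such events to expect cannot be derived from the documents. With 11 planned participants, one affected person is 1/11 = 9% of the cohort, so a single omission would be visible in any safety summary.

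**The case against.** The strongest reply is that the protocol does not rely on this question alone. The Partners alert has safety detection as its stated purpose and covers the setting where serious events are most likely to appear. The KCCQ is given to everyone at baseline and Week 10 and includes a heart failure symptom subset. VIII.B makes the PI responsible for seeing that the team identifies adverse events adequately, and VIII.C and VIII.D provide for weekly discussion and PI review. The study is small, behavioural and delivered mainly by telephone.

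Much of this stands, and it rules out several stronger readings that a reader might infer:

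- *That nothing else collects events, or that every unattributed event goes unreviewed.* The alert, the Week 10 question and the acute symptom handling show otherwise. For the same reason, PI, DSMB and IRB review do not all hang on this one question.
- *That VII.D and VIII.D contradict each other.* Both can be followed as written. The fault is a request narrower than the review it feeds.
- *That Table 1 proves events are not collected, because it has no adverse event row.* The table also omits the alcohol, smoking and readmission questions that the Week 10 text does include, so a missing row shows little.
- *That a low event count would serve as the safety case for the next trial.* The criteria for moving on, in section VI, are feasibility, fit with the qualitative hypotheses and some effect on optimism or positive affect. No event count is among them.

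The reply does not close the remaining gap. The KCCQ yields an outcome score, and nothing says that a worsening score is reviewed as an event. Weekly team discussion handles events already known and does not obtain them from participants.

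**Conclusion.** The point holds in a limited form. VII.D asks participants for less than VIII.D expects the PI to assess, and VIII.B carries a similar limit. Other routes recover Partners admissions and emergency visits, cardiac readmissions reported at Week 10, and acute symptoms that patients volunteer. The types of event listed at the end of the working have no described route to the PI unless the participant blames the study or mentions them unprompted.

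The size is qualitative. Any estimate of events lost would need an event rate and an attribution rate, and the documents give neither.

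The conclusion rests on two readings. First, staff are assumed to put the VII.D question as written. Second, the person to be notified under VIII.B, whose name is masked, is taken to be the PI, to whom that section gives primary responsibility. This is a worthwhile, inexpensive correction to a stated rule; it does not undermine the study's design.

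**What to change.** 1. **VII.D:** replace the request with wording such as: *At each weekly call and at the Week 10 contact, participants will be asked about any new or worsening symptom, fall or injury, emergency visit or hospital stay since the last contact, whatever its cause. The PI will judge relatedness under VIII.D.* Counting from the last contact matters because a participant who completes five sessions may miss others without a protocol deviation.
2. **VIII.B:** change the ongoing notification to cover any adverse event.
3. **IV.B and V.A:** state that admission and emergency alerts, and Week 10 readmission answers, are recorded as adverse events for PI and DSMB review.
4. **Consequential edits:** add the question to Program Content, to the Week 10 call and its paper alternative, and to Table 1.

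The cost is protocol wording and an assumed 1 to 2 minutes per call. Table 1 has nine phone sessions (Weeks 2 to 10) plus the follow-up call, so at most 10 × 1 to 2 = 10 to 20 minutes per participant, or 110 to 220 minutes for 11 participants. More unrelated background events will be recorded and will need the PI's judgement. Expedited IRB reporting of adverse events stays limited to those judged related or possibly related, as VIII.D already provides.
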